**Table 7: Suspension Boundaries for Toxicity During Expansion**

Total Number of Treated Subjects	Suspending Accrual if $\geq$ Number of Subjects with Toxicity
1-5	Not Applicable
6-8	5
9-10	6
11-12	7
13-15	8
16-18	9
19-20	10
21-23	11
24-25	12
26-28	13
29-31	14
32-34	15
35-36	16
37-39	17
40-42	18
43-45	19
46-48	20
49-50	21
51-53	22
54-56	23
57-59	24
60-62	25
63-65	26
66-68	27
69-71	28
72-73	29
74-76	30
77-79	31
80	Maximum enrollment for safety monitoring

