A DLT is defined as a Grade 3 or higher study drug-related or possibly related AE occurring within the first cycle of dosing (excluding Grade 3/4 transient lymphopenia < 14 days in duration, tumor flare defined as local pain, irritation, or rash localized at sites of known or suspected tumor, a transient, reversible  $\leq$  grade 3 infusion AE [ $<$  24 hours], non-clinically significant laboratory abnormalities, or fatigue lasting less than 72 hours) using National Cancer Institute (NCI) Common Terminology Criteria for AEs (CTCAE) version 4.03.

All drug related AEs after Cycle 1 will continue to be collected and evaluated by the Investigators and the Sponsor on an ongoing basis and may be taken into consideration in determining the MTD.

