#### 10.2.1 Expansion Cohorts Safety Monitoring

Bayesian sequential monitoring will be employed to perform ongoing safety monitoring targeting a toxicity rate of not more than 30% (where toxicity follows the same definition as a DLT defined in Section [4.1.2.1](#)) for the first 80 subjects enrolled in the dose expansion phase. Subjects will be monitored across tumor-specific cohorts after a minimum of 6 subjects treated at the selected dose for the dose expansion phase. The criteria for suspending enrollment due to safety are included in [Table 7](#) based on Bayesian sequential monitoring designs by [Thall et al. \(1995\)](#). The determination of the criteria is when:

$$\Pr [\text{prob}(\text{toxicity}) > 0.30 \mid \text{data}] > 0.95.$$

If there is a greater than 95% chance that the toxicity rate is greater than 30%, then accrual will be suspended and the safety review committee will meet to review safety data including aggregated safety summaries. We assume a beta (0.6, 1.4) prior distribution for the toxicity rate,

which has a mean of 0.3 corresponding to the 30% target toxicity rate. A constant 30% rate was chosen for the standard treatment rate.

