### 10.3 Replacement of Subjects

Subjects in the dose escalation phase who do not complete Cycle 1 of treatment for reasons other than a DLT will be replaced to provide sufficient number of subjects included for the dose escalation decision. During dose expansion, subjects will not be replaced.

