### 10.4 Analysis Sets

Safety Population: All subjects who receive at least one dose (or partial dose) of study treatment will be included in the analysis of safety.

DLT Population: All subjects who complete at least one cycle of treatment or discontinue from the study treatment due to DLT will be included.

Pharmacokinetic Population: All subjects in the Safety Population who have relatively complete individual analyte concentration-time profiles that allow for the computation of meaningful PK parameter values.

Response Evaluable Population: Subjects who have measurable disease (per RECIST 1.1) at baseline and also have one post-baseline assessment of tumor response or are withdrawn due to progressive disease/death prior to first response assessment.

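### The Part 2 toxicity suspension rule counts every treated subject, so a subject whose Cycle 1 DLT outcome is never observed is counted as toxicity-free

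*Protocol*

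**What the plan says.** Protocol Section 10.2.1 sets up Bayesian monitoring of toxicity in the expansion phase, "where toxicity follows the same definition as a DLT defined in Section" 4.1.2.1. That section limits a DLT to an event "occurring within the first cycle of dosing". Monitoring begins "after a minimum of 6 subjects treated at the selected dose for the dose expansion phase". Table 7 gives the number of toxicities that suspends accrual, indexed by "Total Number of Treated Subjects". The prior is stated: "We assume a beta (0.6, 1.4) prior distribution for the toxicity rate". Accrual is suspended when the posterior probability of a rate above 0.30 exceeds 0.95.

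Section 10.3 replaces escalation subjects who do not complete Cycle 1 for non-DLT reasons, but adds "During dose expansion, subjects will not be replaced". Section 10.4 (and SAP Section 7) defines a DLT Population: "All subjects who complete at least one cycle of treatment or discontinue from the study treatment due to DLT will be included". Section 10.5.2 uses that population for the DLT incidence table. Section 10.2.1 does not refer to it, and the SAP does not describe the suspension rule.

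**The concern.** A subject informs the DLT rate in one of two ways: by having a DLT, or by being observed through Cycle 1 without one. A subject whose observation ends partway through Cycle 1 with no DLT so far has an unknown outcome. Examples are full withdrawal of consent, loss to follow-up and early unrelated death. Counting by treatment alone adds one to the denominator and nothing to the events for such a subject, exactly as for a completed DLT-free subject. The posterior probability that the rate exceeds 30% is then biased downward.

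The rule exists to catch excess toxicity during expansion. Any loss of sensitivity matters most at moderately excessive rates, such as 40%, where the rule is far from certain to trigger even with complete data.

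**Working it through.** **Inputs.** Prior Beta(0.6, 1.4), threshold 0.95, target 0.30 and start at 6 treated subjects (Section 10.2.1); boundaries (Table 7); operating characteristics (Table 8, maximum 80); planned Part 2 size of about 50 (Section 10.2). The proportion q unobserved in Cycle 1 is not given in the documents, so 1%, 2%, 5% and 10% are assumptions. Loss is taken as independent of toxicity and as happening before a toxicity could be seen.

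**Step 1: reproduce the plan's figures.** After x toxicities in n subjects the posterior is Beta(0.6 + x, 1.4 + n − x). The smallest x giving Pr(rate > 0.30) > 0.95 matches every Table 7 boundary from n = 6 to 79. An exact binomial recursion, checked after each subject up to 80, gives suspension probabilities of 0.0005, 0.0181, 0.2019, 0.7593, 0.9905 and 1.0000 at true rates 0.1 to 0.6. Table 8 prints 0.001, 0.018, 0.202, 0.759, 0.991 and 1.000. Table 8 therefore assumes that every treated subject's outcome is observed.

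**Step 2: what one or a few unobserved subjects can do.**
- 5 toxicities in 8 observed subjects: Beta(5.6, 4.4), probability 0.954, suspend. Add one unobserved subject: 5 in 9, Beta(5.6, 5.4), probability 0.922, no suspension (Table 7 needs 6).
- 19 in 45: Beta(19.6, 27.4), 0.953, suspend. Add five unobserved: 19 in 50, Beta(19.6, 32.4), 0.876, no suspension (Table 7 needs 21).
- 5 in 7 plus one unobserved: 5 in 8, and the boundary is still 5, so suspension is unchanged.

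**Step 3: effect on suspension probability, 50 subjects.** As written, an unobserved subject contributes no event, so the per-subject event probability is p(1 − q). For example, 0.40 × 0.90 = 0.36. With unobserved subjects left out, the number counted is Binomial(50, 1 − q) and each has event probability p. At a true rate of 40%:

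| Assumed unobserved | As written | Left out of the count | Difference |
|---|---|---|---|
| 0% | 0.622 | 0.622 | 0 |
| 1% | 0.603 | 0.619 | 0.016 |
| 2% | 0.583 | 0.616 | 0.033 |
| 5% | 0.522 | 0.606 | 0.084 |
| 10% | 0.422 | 0.587 | 0.165 |

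At 10% unobserved, the other true rates give 0.096 as written against 0.165 left out at 30% (0.173 with complete data), 0.831 against 0.926 at 50%, and 0.984 against 0.997 at 60%.

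**The case against.** The strongest reply is that leaving treatment is not the same as leaving observation. NKTR-214 is given as one infusion on Day 1 of each cycle, so a fully dosed subject has had all of Cycle 1's exposure. Sections 8.2 and 8.5 collect adverse events to 30 days after the last dose, Section 5.3 keeps subjects who stop under safety follow-up, and Section 6.5 ties the end-of-treatment visit to the same 30 days. After one dose, that covers a 14-, 21- or 28-day cycle. Section 6.9 expects toxicity during treatment or within 10 days. This stands. A reader might infer that every early leaver is wrongly counted as toxicity-free, but the documents do not support that: a leaver with a DLT counts as a toxicity, and a leaver followed through the window is a genuine non-event.

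A reader might also blame the no-replacement rule, or the contrast with Part 1. Neither is the cause. A replacement would add another treated subject and remove none. Part 1 replaces subjects so that the escalation decision has enough of them.

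It is also fair to say that suspension is not always delayed. Boundaries are flat over two or three subjects, so one unobserved subject often changes nothing. In one corner the treated count even triggers sooner: 5 toxicities in 5 observed subjects plus one unobserved reaches the 6-subject minimum. Finally, Section 10.2.1 has a safety review committee meeting at least quarterly, and Section 6.9 requires DLT-criteria events to be reported within 24 hours.

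These points limit the size of the problem. They do not supply the missing rule for a subject whose outcome is unknown.

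**Conclusion.** The gap is real but narrow. Section 10.2.1 and Table 7 have no evaluability condition, and nothing in the SAP adds one, so subjects with unknown Cycle 1 DLT status enter the posterior as non-events. The cause is the treated denominator.

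The size depends on a rate that the documents do not give. With 50 subjects and a true 40% rate, 1–2% unobserved lowers the suspension probability from 0.622 to 0.603–0.583, a modest loss. At 5% and 10% it falls to 0.522 and 0.422. Given the 30-day follow-up, the higher figures should be read as the upper part of an assumed range and not as an expectation. They also assume that loss is unrelated to toxicity and comes before any toxicity could be seen. The effect is small at a true 60% rate.

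**What to change.** In Section 10.2.1 and the Table 7 column heading, replace the treated count with subjects of known Cycle 1 DLT status. That means every subject with a toxicity, whatever the recorded reason for leaving, plus every subject observed through the end of the DLT window without one. Leave out only subjects whose status is unknown because observation ended early. The same sentence should say when a subject still in Cycle 1 enters the count. Boundaries and the no-replacement rule stay unchanged.

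Two simpler wordings should be avoided:
- **Dropping all leavers without a toxicity** would discard genuine non-events while keeping all toxicities. If 10% leave but are fully observed, the monitored rate at a true 30% becomes 0.30 / (1 − 0.10 × 0.70) = 0.323. With 50 subjects, the chance of suspension at that acceptable rate rises from 0.173 to 0.206, 0.243 and 0.287 at 5%, 10% and 15% such leavers.
- **Citing the DLT Population** could omit a subject who had a DLT but left for another recorded reason.

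The cost is one sentence and a column heading. The count rises slightly more slowly, so suspension is slightly more likely at a given number treated. At a true 30% rate with 10% unobserved it is 0.165, still below the 0.173 that the rule gives with complete data.

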**1.0 STUDY SYNOPSIS**

Name of Sponsor:	Nektar Therapeutics
Name of Finished Product:	NKTR-214 drug product
Name of Active Ingredient:	NKTR-214 drug substance
Title of Study:	A Phase 1/2, Open-label, Multicenter, Dose Escalation and Dose Expansion Study of NKTR-214 in Subjects with Locally Advanced or Metastatic Solid Tumor Malignancies
Duration of Treatment:	Subjects will be treated until unacceptable toxicity, or disease progression per Response Evaluation Criteria in Solid Tumors (RECIST) version 1.1 (treatment may continue if there is clinical benefit as determined by the Investigator).
Phase of Development:	Phase 1/2
Objectives:	
The primary objectives are:
 
 
To evaluate the safety and tolerability, and define the maximum tolerated dose (MTD) of NKTR-214
 
To evaluate the efficacy of NKTR-214 by assessing the objective response rate (ORR) at the MTD or the dose below the MTD
 
 
The secondary objectives are:
 
 
To evaluate the efficacy of NKTR-214 by assessing best overall response (BOR), [REDACTED] duration of response (DOR), clinical benefit rate (CBR), time to response (TTR), [REDACTED]
 
To characterize the pharmacokinetic (PK) profile of NKTR-214 and relevant metabolites
 
To assess the immunogenicity of NKTR-214
 
 
The exploratory objectives are:
 
 
To assess the immunologic effect of NKTR-214 in tumor tissue on tumor-infiltrating lymphocytes (TIL)
 
To assess the immunologic effects of NKTR-214 in blood, including effects on cytokines, natural killer (NK) cells, T-cells, and other serum proteins and immune modulators
 

Study Population	Adults age 18 and older with histologically confirmed locally advanced or metastatic solid tumors in Part 1 (Dose Escalation) and renal cell carcinoma (RCC) in Part 2 (Dose Expansion) who have measurable disease
Number of Subjects (planned):	
Part 1: Approximately 50 subjects will be enrolled into the dose escalation phase of the study.
 
Part 2: Approximately 50 subjects will be enrolled into the dose expansion phase of the study.

Number of Study Sites:	Approximately 3 clinical study sites for dose escalation cohorts; up to 15 additional sites may be added for the dose expansion cohort.
Countries:	USA

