### **6.3 Treatment Period**

Subjects who meet the selection criteria may start NKTR-214 treatment within 28 days following the Screening visit. The treatment period of the study is divided into multiple 21-day cycles with associated evaluations and procedures. Results of the assessments must be reviewed and documented before administering the first dose of the next cycle. No subject will be permitted escalation of dose level after assignment to a specific NKTR-214 dose level. Dose reductions after Cycle 1 due to AEs may occur following a discussion with the site Investigator and Medical Monitor. Every effort should be made to schedule visits within the protocol-specified windows.

For each dose level in Part 1, the first subject enrolled into a given dose cohort will be treated and monitored from Cycle 1, Day 1 through Cycle 1, Day 5 for safety and tolerability prior to dosing of additional subjects at that dose level.

Cycle 1, Day 1 will be the first day of treatment with NKTR-214 and Cycle 2, Day 1 will be the first day of the second dose of NKTR-214. Results from Day 1 laboratory evaluations must meet eligibility criteria prior to Cycle 1, Day 1 dosing.

During dose escalation, subjects who drop out prior to completion of Cycle 1 will be replaced unless the subject discontinued due to a DLT. During dose expansion, subjects will not be replaced.

Subjects will be treated until unacceptable toxicity, or disease progression per RECIST version 1.1. In the presence of disease progression, treatment may continue if there is clinical benefit as determined by the Investigator based on a reduction of symptoms related to cancer and absence of clinical deterioration or decline in ECOG performance status.

Note: Dosing may change to q14d or q28d following review and agreement by the Sponsor and Investigators. The change in cycle length will be determined by review of safety data and PK review of study drug.

After completing the pre-dosing procedures, administer NKTR-214 as an IV infusion over  $15 \pm 5$  minutes (Section 6.11).

Postdosing:

- The study site must be equipped for medical emergencies and have access to an intensive care unit.
- During dosing days, subject will stay in clinic for observation approximately 1 hour after dosing.
- Administer at least 2 liters of fluid (IV or self-administered orally [e.g., fluid containing electrolytes]) during Days 1 to 5 of every cycle.

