**Table 8: Operating Characteristics for Subject Accrual Suspension Rules**

True Toxicity Rate	Accrual Suspension Probability	Achieved Sample Size		
		25th	50th	75th percentiles
0.1	0.001	80	80	80
0.2	0.018	80	80	80
0.3	0.202	80	80	80
0.4	0.759	14	34	80
0.5	0.991	7	14	25
0.6	1.000	6	8	14

An internal safety review committee consisting of representatives from Clinical Development, Drug Safety, Biostatistics, other functional representatives, as needed, and at least one Principal Investigator will meet at least quarterly to review safety data for potential safety risks or more frequently if needed. If it is determined there is a high probability of observing more than 30% toxicities, enrollment will be suspended and the safety review committee will be convened to make a recommendation on the continuation, modification, or discontinuation of the study.

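### Part 2 toxicity monitoring sets first-cycle DLTs against all subjects treated, with no rule for those still in Cycle 1, so overlapping enrolment can step over a Table 7 boundary

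*Protocol*

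**What the plan says.** **The rule.** Protocol Section 10.2.1 suspends accrual when the posterior probability that the toxicity rate exceeds 0.30 is above 0.95, under a beta(0.6, 1.4) prior. Table 7 turns this into counts. Its row index is "Total Number of Treated Subjects", and looks begin "after a minimum of 6 subjects treated at the selected dose".

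**The event.** Section 10.2.1 borrows the Part 1 definition ("where toxicity follows the same definition as a DLT defined in Section" 4.1.2.1). That section defines a DLT as an event "occurring within the first cycle of dosing". Section 6.3 says "The treatment period of the study is divided into multiple 21-day cycles", and the schedule may change to 14 or 28 days.

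**Enrolment.** The Day 1 to 5 hold for the first subject and the full-cycle wait between cohorts (Sections 4.1.2.1 and 6.3) belong to dose escalation. No equivalent is stated for Part 2, where the synopsis says "up to 15 additional sites may be added for the dose expansion cohort".

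**What is not said.** Section 10.2.1 does not say how subjects still in Cycle 1 are counted. Section 10.4 defines a DLT Population (one cycle completed, or discontinued because of a DLT), but nothing ties it to Table 7. Table 8 gives an "Accrual Suspension Probability" and achieved sample sizes without an accrual rate or outcome delay. The SAP does not mention the rule.

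**The concern.** Numerator and denominator run on different clocks. The denominator rises on the day of dosing; the numerator may take a full cycle to catch up. Every subject in between is credited as a non-event, which pulls the posterior down and moves the reading to a row with a higher boundary. This needs no dropouts and no missing data, only overlap.

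At stake is the one numerical safety trigger in Part 2. If it fires later or less often than Table 8 indicates, more subjects are dosed at a too-toxic dose before the committee is convened, and the gap widens with faster accrual.

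**Working it through.** **1. Table 7.** With x DLTs in n subjects the posterior is Beta(0.6 + x, 1.4 + n − x). The boundary is the smallest x with Pr(rate > 0.30) > 0.95. This reproduces Table 7 at every n from 6 to 79.

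**2. Table 8.** An exact recursion, one subject at a time, with each outcome known before the next dose and a maximum of 80:

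| True rate | Table 8 | Exact | Table 8 quartiles | Exact quartiles |
|---|---|---|---|---|
| 0.1 | 0.001 | 0.0005 | 80/80/80 | 80/80/80 |
| 0.2 | 0.018 | 0.018 | 80/80/80 | 80/80/80 |
| 0.3 | 0.202 | 0.202 | 80/80/80 | 80/80/80 |
| 0.4 | 0.759 | 0.759 | 14/34/80 | 14/34/78 |
| 0.5 | 0.991 | 0.991 | 7/14/25 | 8/14/25 |
| 0.6 | 1.000 | 1.000 | 6/8/14 | 7/8/14 |

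The probabilities agree and the quartiles are within 2 subjects, with no delay in the calculation.

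**3. Stepping over a boundary (no accrual assumption needed).**
- 5 DLTs in 8: Beta(5.6, 4.4), posterior 0.954, boundary 5. Suspend.
- Same eight subjects, but 9 to 11 dosed before the fifth DLT appears: 5 in 11, Beta(5.6, 7.4), posterior 0.829, boundary 7. Continue.

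**4. Reference at the planned size.** Part 2 plans about 50 subjects. The same exact recursion stopped at 50 gives 0.173, 0.622 and 0.947 at true rates 0.3, 0.4 and 0.5. The fall from 0.759 to 0.622 is due to 50 versus 80 subjects and is a separate matter. The loss from pending outcomes is measured from 0.622.

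**5. Size of the loss.** Assumptions: Poisson accrual at 2, 4 or 8 per month, 50 subjects, no dropouts, and DLT onset uniform over 21 days or within 10 days (Section 6.9 calls toxicity most likely during treatment or in the 10 days after it). The mean number inside a 21-day cycle is rate × 21/30.4 = 1.4, 2.8 or 5.5. There were 6000 runs per cell (standard error at most √(0.25/6000) = 0.0065); repeat runs differed by about 0.01 to 0.02. Boundary crossings during the last subjects' Cycle 1 are counted.

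| Accrual per month | 2 | 4 | 8 |
|---|---|---|---|
| 40% toxicity, 21-day onset, as written | 0.61 | 0.58 | 0.53 |
| 40% toxicity, 10-day onset, as written | 0.61 | 0.60 | 0.58 |
| 50% toxicity, 21-day onset: median treated, as written | 15 | 18 | 22 |
| 50% toxicity, 21-day onset: median treated, with the fix | 14–15 | 16 | 17 |

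The loss at 40% is 0.622 − 0.61 ≈ 1 point up to 0.622 − 0.53 ≈ 9 points. With a 28-day cycle and onset spread over it, the values are 0.60, 0.56 and 0.51. At 50% toxicity the suspension probability falls by about 2 points or less.

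**6. Sensitivity to the counting convention.** If only crossings before the last subject is dosed count, the as-written rule at 50 subjects and 40% toxicity (21-day onset) gives 0.589, 0.562, 0.530 and 0.408 at 1, 2, 4 and 8 subjects per 21 days; at 50% toxicity it gives 0.940, 0.926, 0.907 and 0.855. Part of that drop cannot be recovered by any rule, because some outcomes arrive after accrual has closed.

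**7. Does the fix work?** Testing every k in treatment order gives 0.61–0.63 at 40% (exact 0.622) and 0.16–0.19 at 30% (exact 0.173) across the scenarios. Once all outcomes are in, it has suspended on exactly the sequences that the immediate-outcome calculation suspends on. Substituting the DLT Population as denominator overshoots: at 30% toxicity and a maximum of 80 it gives about 0.24–0.31 against 0.202, because DLTs enter at once and non-DLTs only at the end of the cycle.

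**The case against.** **The reading is inferred.** The criterion is a posterior given the data, and a subject dosed yesterday has supplied none. No sentence says pending subjects count as toxicity-free, and a DLT Population exists. This stands as a limit: a reader might infer that the plan deliberately scores them as non-events, and it does not say so. But it prints treated subjects as the index and offers no other count, so the literal rule is the one that sites and the committee would apply.

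**There is other protection.** A reader might infer that Table 7 is all that guards Part 2. It is not. A safety committee meets at least quarterly, or sooner if needed (Section 10.2.1), DLTs are reported within 24 hours (Section 6.9), and the sponsor may suspend the study at any time (Section 11.0). Table 7 is the only numerical trigger, however, and a quarter spans about four 21-day cycles. A boundary missed once may also be crossed at a later DLT, so one missed look is not a failed rule.

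**The size rests on an assumed accrual rate.** Correct. With onset within 10 days the loss is about 1 to 4 points, and at 2 per month with a 21-day cycle it is small under either onset pattern.

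**The fix has its own cost.** It gives no weight to DLT-free follow-up in subjects after the k-th, so it can suspend when the posterior over all treated subjects is below 0.95. That is true, and other pending-outcome rules could be defended. The consequence is a pause for committee review, at the false-suspension rate already designed in.

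**Conclusion.** The point holds as a gap in the rule's definition with a quantifiable effect. Read literally, the Part 2 rule can step over a boundary, and Table 8's suspension probabilities describe immediate outcomes. Under the assumed 2 to 8 subjects per month, 50 subjects and a 21-day cycle, the loss at 40% true toxicity is about 1 to 9 points from 0.622. At 50% toxicity the cost is mainly exposure: relative to the corrected rule, a median of roughly 0 to 1, 2 and 5 more subjects treated at 2, 4 and 8 per month.

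Two stronger readings are not supported. The whole distance from Table 8's 0.759 cannot be charged to pending subjects, since most of it comes from the smaller planned enrolment. Nor can a median of 14 treated at 50% toxicity be recovered when outcomes are delayed: the corrected rule delivers about 14 to 17. The change is worth making before Part 2 enrols, because it is cheap and removes the dependence of the suspension probability on accrual speed.

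**What to change.** In Section 10.2.1, replace the single look with wording such as:

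> Subjects are numbered in order of first dose. When the sixth subject is dosed, and at each new DLT after that, accrual is suspended if, for any k from 6 to the number treated, the DLTs observed so far among the first k subjects reach the Table 7 boundary for k.

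The check at the sixth dosing covers five DLTs in the first five subjects, which would otherwise wait for a further DLT. Table 7 itself is unchanged. Label Table 8's achieved sample sizes as assuming immediate outcomes, or re-run them with the planned accrual rate and cycle length.

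**Cost.** Two or three sentences and, if chosen, one simulation; no extra subjects, visits or data. Suspension at a true 30% rate returns from about 0.09–0.16 to the designed 0.17 (50 subjects), re-run sample sizes will look slightly less favourable, and some suspensions will occur with an all-treated posterior below 0.95.
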